6. State inclusion criteria for enrollment in study:

Inclusion Criteria include: 1. Age 18 years or older, 2. Discharge from inpatient unit for suicidal ideation or attempts, or placement on the high-risk suicide list maintained by suicide prevention coordinators, or patient from outpatient service that meets criteria of 4 or 5 on CSSRS or attempt within the past year 3. Concurrence from the patient's mental health provider for the Veteran to participate in the study and the provider is willing to work with the research team.

7. State exclusion criteria for enrollment in study:

Exclusion Criteria include: 1. Unable to provide informed consent or complete study requirements, 2. Unable to speak English, 3. Cognitive difficulties that impair consent Capacity, 4. Unable or unwilling to provide at least one verifiable contact for emergency or tracking purposes, 5. Unable to attend outpatient group treatment program or tolerate group therapy format, 6. Active alcohol or opiate dependence requiring medically supervised withdrawal, 7. Schizophrenia diagnosis, 8. Participation in another intervention RCT.

8. Will vulnerable subjects be enrolled in this study?

YES	X	NO	
------------	----------	-----------	--

	YES	NO
Individuals with lack of decision-making mental capacity		X
Economically/socially disadvantaged persons	X	
Educationally disadvantaged persons	X	
Pregnant women, for minimal risk only		

Fetuses Requires Medical Center Director authorization. See IRB SOP.

Children Requires Medical Center Director authorization. See IRB SOP.

Prisoners Requires CRADO authorization. See IRB SOP.

If Yes for any answer, provide a means by which vulnerability is determined: **Vulnerability will be determined through gathering basic demographic data of each participant. James J. Peters VA Medical has a population of veterans who are economically, socially, and educationally disadvantaged; thus, the PI anticipates recruiting from vulnerable populations.**

9. Are prospective subjects likely to feel vulnerable to coercion or undue influence to enter the study?

YES		NO	X
-----	--	----	---

a. Are there any payments to subjects?

YES	X	NO	
-----	---	----	--

b. If No, proceed to question 9.c.

How much are the payments? **\$50-\$75**

Provide a schedule (timing) of payments. **Baseline, post intervention, 3 months post completion of intervention, 6 months post completion of intervention**

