As mentioned above, upon hearing the description of the study, the participant will be required to describe the procedures to the person obtaining consent, summarize what is expected of him or her and list two risks involved. This will ensure that participants understand the implications of their decision to participate and are able to make a well-informed decision and communicate this decision to the person obtaining consent. Consent will be obtained in a private setting by an investigator to minimize any power differential that the participant might feel. Participants unable to communicate with the investigator for any reason will not be included in the study. Only subjects having the capacity to give informed consent will be enrolled in the study. The recruitment process will not be coercive or unduly influencing, as participants enter the research study voluntarily and understand that they have the right to withdraw at any time. Subjects will be told that non-participation in the study will not affect any current treatments they are receiving at VA or elsewhere.

13. Summarize what actually will be done to the subjects during their participation in the study:

The subject will fill out the informed consent. They will then fill out a series of clinician interviews and self-report measures asking questions related to thoughts and feelings about suicide, general mental and physical health, and relationship with other. After these are completed half the group will be randomized to the PLF intervention arm in which Veterans will participate in the 10 weekly groups.

a. Provide a clear description of what is being done for research purposes and what is being done as part of "usual care":

For research purposes: Initial consult with research investigators and consenting, which will take approximately 30 – 45 minutes, completing assessments (1.5 hours) and answering interview-style questions pertaining to the research topic (30 minutes).

Subject matter of the interview includes: communication quality with others, overall life satisfaction, frequency of suicidal ideation or urges, and reasons for attempting suicide.

“Usual care”: Subjects will be able to continue all regular treatment outside of the study.

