b. Provide a detailed **list of tests and procedures** that will be performed for research purposes (e.g., blood tests, urine tests, cultures, interviews, questionnaires, surgical procedures, cardiac catheterization, pulmonary function tests, X-rays, scans, etc) during the course of the study. **List must indicate tests and procedures only for subjects who sign a VA consent form, regardless of where tests and procedures take place:**

Test /Procedure:	Where:	Performed by Whom: (Insert Name or TBD if not yet known)	When:	# of times:
Columbia Suicide Severity Rating Scale (CSSRS)– current & since last visit version	Research office	[name], [name]	0, 3, 6,12, weekly for PLF group participants	4
Access to Lethal Means	Research office	[name], [name]	0, 3, 6,12	4
Beck Depression Scale	Research office	[name], [name]	0, 3, 6,12	4
Beck Hopelessness Scale	Research office	[name], [name]	0, 3, 6,12	4
Self-report log based on the Modified Cornell Services Index (MCSI)	Research office	[name], [name]	0, 3, 6,12	4
Brief Survey of Safety Plan Utilization (BSSPU)	Research office	[name], [name]	0, 3, 6,12	4
Suicide-Related Coping Measure (SRCM)	Research office	[name], [name]	0, 3, 6,12	4
Group Psychotherapy Process Measure*	Research office	[name]	1,5,10 (weeks)	3

PLF treatment arm only		[name]		
Buss-Perry Aggression Questionnaire	Research office	[name], [name]	0, 3, 6,12	4
Reasons for Living	Research office	[name], [name]	0, 3, 6,12	4
Attitudes Towards Seeking Professional Psychological Help	Research office	[name], [name]	0, 3, 6,12	4
Insomnia Severity Index	Research office	[name], [name]	0, 3, 6,12	4
Beck Lethality Scale	Research office	[name], [name]	0, 3, 6,12	4
The Self-Injurious Thoughts and Behaviors Interview	Research office	[name], [name]	0, 3, 6,12	4
Suicide Intent Scale	Research office	[name], [name]	0, 3, 6,12	4
Beck Scale for Suicidal Ideation	Research office	[name], [name]	0, 3, 6,12	4
Barratt Impulsiveness Scale	Research office	[name], [name]	0, 3, 6,12	4

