Participants will be carefully monitored during the interview by the research staff who will be trained in noticing when the participant is uncomfortable or needs to take a break. In addition, research staff will follow-up via phone call with participants within a day of the interview to check in and assure the participant is not experiencing any delayed distress. Participants who demonstrated distress during the interview will be closely monitored through follow-up phone calls and the PI and RA will notify the primary provider of the participant's experience during the interview.

c. Provide a plan for periodic review of safety of research subjects and data:

All risks and potential complications are discussed with the subjects during consent signing, and any new information regarding risks will be provided by phone immediately. Patients are monitored closely and should any unanticipated findings arise, the IRB will be notified.

PI (MG) will be available to perform a suicide assessment at any point a rater or clinicians delivering PLF suspects that a subject is at risk for suicide as determined through clinical questioning or a research instrument assessing suicidal intent. The senior clinicians will ask questions regarding suicidal ideation and suicide plan and arrange for transfer to the psychiatric emergency room and/or inpatient stabilization at the JJPVA should imminent suicidal behavior manifest itself. All suicide attempts and deaths will be reported to the JJPVA and the DSMB assembled for this study.

d. Describe how you will determine whether the study should be continued in light of emerging information:

The PI will work in conjunction with the IRB to evaluate any emerging information and determine if and how the study should be continued.

e. Is there a Data Monitoring Committee (DMC) or a Data Safety Monitoring Board (DSMB)?

DMC	X	DSMB		NO	
-----	---	------	--	----	--

If no, proceed to question 17.

Describe your DMC or DSMB, including frequency of reporting:

2018/2019 – Quarterly. 2020 onwards, biannually (January and July)

Describe how the DMC or DSMB will communicate with the IRB: **Reports submitted to IRB on this basis: 2018/2019 – Quarterly. 2020 onwards, biannually (January and July)**

17. Data Analysis and Sample Size:

a. Describe the analysis that will be performed on the data:

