For the survival analysis comparing the PLF and TAU treatment conditions, we assumed a 20% dropout in both groups based on previous safety planning data to date using SAFE-VET, exponential hazard functions, and considered four scenarios of suicide behavior reduction of PLF over TAU. We assumed a base rate of 49% for SB in the TAU group based on published data from ED-SAFE. The sample sizes needed for 80% power were calculated using the “Proc Power” procedure from SAS software © 2002- 2012. In the absence of pilot data, we used a published formula for the Variance Inflation Factor from the weighted log-rank test, to adjust the required sample size for within-group, and within-clinician, dependence. We assumed m=5 subjects per group or clinician, and an ICC for suicidal behavior within the group of r=0.01 based on literature. While power analyses were calculated for several reduction rates, we selected the 35% reduction rate as the most reasonable estimation for the reasons outlined below. The composite suicide behavior outcome has minimal data outside of ED-SAFE’s reduction of 18% in non-veterans recruited from an emergency room. Stanley and Brown’s SAFEVET data on Veterans presenting to an ED, reported a 45% reduction in suicide attempts (however the composite definition of suicidal behavior was not used). Moreover we anticipate PLF to have increased potency over SAFEVET due to the group setting and greater number of in-person sessions. Balancing the enhanced potency of the PLF intervention with the new composite definition of SB, the 35% reduction scenario is reasonable. Therefore, we expect the reduction to be above the minimum values indicated, and are confident that N=145 will provide ample power for this aim. Then, the research team included an additionally 35 to be consented who would likely not screen into the study or meet inclusion/exclusion criteria.

18. Community-based Participatory Research

Is this research based on Community-based participation?

YES		NO	X
------------	--	-----------	----------

If Yes, answer questions (a-h). If No, proceed to Question 19.

a. Describe the community that will be involved in this research:

b. What is the role of the community in this research?

c. Does this research include a community organization that is engaged in research?

YES		NO	
------------	--	-----------	--

If Yes, does that organization have a Federal Wide Assurance (FWA)?

YES		NO	
------------	--	-----------	--

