Title: **Group ("Project Life Force") vs. Individual Suicide Safety Planning RCT**

NCT Number: **NCT03653637**

Date: **05/12/2025**

Primary Statistical Analysis Plan

The primary outcome of suicidal behavior will be analyzed using a Cox Proportional Hazard Regression, with treatment condition (PLF+TAU vs. TAU) and baseline suicidal behavior level as predictors, and incidence and time to the first suicidal behavior during the study course as the outcome variables. The model will adjust for treatment site. Kaplan-Meier estimates of the cumulative hazard function for both groups will be graphed and the proportionality assumption checked. If the hazard functions are not proportional, the non-parametric log-rank test will be used instead, with treatment condition as predictor, and we will use a sensitivity analysis to test the effect of baseline suicidal behavior severity by splitting the treatment conditions by the presence/absence suicidal behavior.

Most secondary and other outcomes (depression, hopelessness, thwarted belongingness, aggression dimensions, insomnia and suicide-related coping) will be analyzed in Linear Mixed Effects (LME) regression models. All LMEs will be adjusted for site and will include randomization condition, time, and a randomization by time interaction. The treatment effect of PLF+TAU vs TAU will be the treatment by time interaction. Time will be treated as a linear variable. Mixed-effect models can be fit to data with dropout or missing values as long as the data is missing at random, thus, attrition does not necessarily reduce the number of participants included in these analyses.

For the two outcomes (drug and alcohol use) that are only measured at the one-year follow-up (with retrospective questions about the past 12 months), we will compare between PLF+TAU and TAU with t-tests or Mann-Whitney U tests where appropriate.

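### The CSSRS look-back has no defined anchor and is given weekly in PLF only, so ascertainment of the primary endpoint can depend on arm

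*Protocol*

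**What the plan says.** The CSSRS row in protocol section 13.b names the "current & since last visit version" and gives the timing as "0, 3, 6,12, weekly for PLF group participants", with a count of 4 administrations. It does not say which version is used at which contact, or whether the last visit is the last research assessment or the last group session. No unit is printed for 0, 3, 6 and 12. Months is the natural reading, because participation lasts 12-14 months (section 4.f) and another row of the same table labels weeks explicitly.

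Section 13 states that in the intervention arm "Veterans will participate in the 10 weekly groups". No weekly CSSRS is scheduled for TAU.

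The SAP takes "incidence and time to the first suicidal behavior during the study course as the outcome variables". It names no instrument or data source for that endpoint, and neither includes nor excludes the weekly forms.

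The payment schedule in section 9 gives different assessment times: "Baseline, post intervention, 3 months post completion of intervention, 6 months post completion of intervention".

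**The concern.** A since-last-visit form asks about the interval since an earlier contact. When one arm has up to 10 additional contacts with the same instrument, the interval covered and the number of chances to detect an event both depend on randomized arm, unless the protocol fixes the anchor and the SAP fixes the data source. Neither does.

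The two open choices pull in opposite directions. Counting the weekly forms favors detection in PLF. Leaving them out, while raters at month 3 ask only about the time since the last session, would leave the treatment weeks covered in TAU and uncovered in PLF. Restricting the endpoint to the common visits is an obvious remedy for the extra weekly detection. With the anchor undefined, that remedy could replace one bias with its opposite.

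**Working it through.** The documents state no look-back length, so there is no planned figure to reproduce. The check has three parts.

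**1. Contacts.** TAU has 4 CSSRS contacts. PLF has 4 + 10 = up to 14. The documents give no per-contact detection probability, so the bias from extra detection has a direction but no computable size.

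**2. Look-back at month 3.** Month 3 = 3 × 365.25 / 12 / 7 = 13.04 weeks.

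| Meaning of last visit | Last PLF session | PLF look-back | TAU look-back |
|---|---|---|---|
| Previous research assessment | not relevant | 13.0 weeks | 13.0 weeks |
| Last group session, no start lag | week 9 or 10 | 4.0 or 3.0 weeks | 13.0 weeks |
| Last group session, 1-week lag | week 10 or 11 | 3.0 or 2.0 weeks | 13.0 weeks |
| Last group session, 2-week lag | week 11 or 12 | 2.0 or 1.0 weeks | 13.0 weeks |
| Last group session, 4-week lag | week 13 or 14 | about 0 | 13.0 weeks |

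Start lag is not stated. Missed final sessions would lengthen the PLF look-back.

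**3. Size under the adverse combination** (anchor at the last session, weekly forms not counted, no other source used). Inputs from section 17.b: "We assumed a base rate of 49% for SB in the TAU group", and exponential hazards. Assumptions: 49% is a 12-month rate (no time frame is given), both arms have the same true hazard, and the tenth session falls at week 10.

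- Hazard: −ln(1 − 0.49) = 0.673 per year.
- First event by week 10: 1 − exp(−0.673 × 10/52.18) = 12.1%, which is 12.1/49.0 = 24.7% of the year's first events.
- First event by month 3: 1 − exp(−0.673 × 13.04/52.18) = 15.5%. About 78% of these fall in the session weeks.
- Recorded at month 3 in PLF with a 3.04-week look-back: 1 − exp(−0.673 × 3.04/52.18) = 3.9%, against 15.5% in TAU.
- Recorded by 12 months in PLF if later events occur at the same rate: 1 − exp(−0.673 × 42.18/52.18) = 42.0%, against 49.0%. The spurious relative reduction is 1 − 42.0/49.0 = 14%.

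The table gives the large-sample Cox hazard ratio with no true effect, PLF events before week 10 hidden and censoring at 12 months. It varies the hazard of a further behavior in those whose early event was hidden.

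| Later hazard, relative to baseline | Apparent HR |
|---|---|
| 0 (never recurs) | 0.65 |
| 1 | 0.76 |
| 2 | 0.83 |
| 3 | 0.88 |
| 5 | 0.93 |

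For scale, the 35% reduction planned in section 17.b takes 49% to 49 × 0.65 = 31.9%. Under the same exponential model that is a hazard ratio of ln(0.6815)/ln(0.51) = 0.57.

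**The case against.** A reader might infer that the month-3 form does look back only about three weeks in PLF, that early PLF events are therefore hidden, and that the trial is biased toward PLF. The documents do not support that. It needs three conditions together, and none is stated.

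- The last visit must mean the last group session. The count of 4 in the CSSRS row matches the four research assessments, and the 10 group sessions have their own row. Anchoring to the previous research assessment is at least as natural, and the weekly form might be the current version.
- The weekly forms must be left out. The SAP counts first behavior over the whole study and plans no restriction to common visits. If the weekly forms count, consecutive forms cover PLF continuously from baseline, and the asymmetry becomes over-detection in PLF.
- No other source may supply the early events. "The Self-Injurious Thoughts and Behaviors Interview" is listed at 0, 3, 6 and 12 with no weekly use, and section 16.c says that "All suicide attempts and deaths will be reported to the JJPVA and the DSMB".

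These objections remove the claim that events are hidden. They do not remove the ambiguity. No passage makes the second interview or the safety reports a source for the primary endpoint, the quoted safety sentence names only attempts and deaths, and the recall period of the second interview is not given. The count of 4 also cuts both ways: it fits a reading in which the weekly forms are not research data.

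The objection to the size also stands in part. The 0.65 figure assumes that nobody with an early behavior has another within the year, which is hard to believe in this population. The upper part of the range is more credible.

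**Conclusion.** The point holds as a gap in definition, not as a demonstrated bias in a known direction. Protocol and SAP together leave the look-back anchor, the version used at each contact and the status of the weekly forms undefined, for an endpoint whose detection depends on all three.

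- **Weekly forms counted:** up to 14 contacts in PLF against 4 in TAU. PLF events tend to be found more often and dated earlier, which works against PLF. The size cannot be computed from the documents.
- **Weekly forms not counted, month-3 form anchored to the last session:** look-back of about 0 to 4 weeks against 13, and an apparent hazard ratio of about 0.65 to 0.93 with no true effect. This rests on 49% being a 12-month rate, constant hazard, a tenth session at week 10 and no other source of events.
- **Raters ask both arms back to the previous research visit, and only those interviews count:** the windows match and there is no look-back bias.

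The issue deserves correction because the endpoint is primary and the remedy is cheap.

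**What to change.** In protocol section 13.b, state that the research CSSRS at 3, 6 and 12 asks participants in both arms about the whole period since their previous completed scheduled research assessment, regardless of any weekly group form, and records the date of each behavior. State which version is used at each contact, print the unit of the schedule, and reconcile it with the payment schedule in section 9, since the visit times set the windows.

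In the SAP, derive the primary endpoint from these common interviews. Use behaviors detected only on weekly PLF forms in a sensitivity analysis.

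The month-3 window is then about 13 weeks in each arm. The cost is a few sentences in the protocol, rater instructions and SAP, with no added visits; PLF participants repeat a few questions at month 3. The weekly contacts themselves remain, so any effect of repeated questioning on PLF participants' later recall is not removed.

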Interpersonal Needs Questionnaire	Research office	[name], [name]	0, 3, 6,12	4
Mini-International Psychiatric interview (MINI)	Research office	[name], [name]	0	1
McLean Screening	Research office	[name],	0	1

Instrument for BPD		[name]		
PLF Intervention Sessions	Research office	[name]	Weekly	10
Moral Injury Outcome Scale (MIOS)	Research office	[name], [name]	0, 3, 6, 12	4

c. If laboratory tests are part of this protocol, will some or all study-related tests be performed outside this medical center?

YES	NO	N/A	X
-----	----	-----	---

d. Provide a statement that defines who will be financially responsible for the costs associated with participation in the study (e.g., examinations, procedures, drugs, devices, etc.) and a statement that defines what will be provided without cost to the subjects:

The patient will not incur any costs from participating in this study. The PLF intervention will be provided free of charge. In the event of an injury resulting from the research study the facilities of the Bronx VA will be made available to patients.

List all Authorized Prescribers of drugs (whether or not the drug is investigational)

NA

e. VHA Health Record (If yes to (i) below or if clinical resources are to be used, a VHA health record must be created in CPRS [VHA Handbook 1200.05 #29j]).

(i) Will the research intervention possibly lead to physical or psychological adverse events?

YES	X	NO	
-----	---	----	--

(ii) Do you have a process in place to include a copy of the signed informed consent and HIPAA authorization in the medical record for the type research described above for each subject?

YES	X	NO	
-----	---	----	--

If yes, Please describe: **A copy of each consent is scanned into subjects' charts and a hard copy is retained in study records.**

(iii) Did the IRB determine that CPRS flagging is required?

YES	NO	X	
-----	----	---	--

14. Risks:

a. Identify study risk:

No Risk	
Minimal Risk	
Greater Than Minimal Risk	X

b. Describe the steps you could take to minimize risk to subjects, *without changing the science* of the study:

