For investigational drugs, what are the possible risks associated with the study drug relative to possible interactions with medications likely to be used by subjects? **NA**

What will your approach be to such risks? **NA**

Will such subjects be excluded from the study? **NA**

Have you reviewed scientific literature or relevant FDA and Sponsor Advisories alerts or warnings relevant to this medication/device? **NA**

YES		NO	
------------	--	-----------	--

If there was any new information, what were the possible risks to subjects based on this information? **NA**

If there was any new information, how were potential benefits for subjects affected by this information? **NA**

If new information is received from the FDA or Sponsor that may affect the conduct of this study, would you be willing to change the study design or study procedures?

YES		NO	
------------	--	-----------	--

How will you inform subjects of any relevant information from the FDA or Sponsor Advisories? **NA**

What advice will you provide to subjects if there are questions on continuing participation in the study? **NA**

16. Research Safety:

a. Describe your Data Safety Monitoring Plan for subjects (3-4 sentences):

Data Monitoring Committee (through Hines VAMC in Chicago, IL)

b. What information will you be collecting for AEs/SAEs and what is your plan for reporting these to the IRB?

Subjects will be monitored by a study psychiatrist for symptomatic assessment, status of clinical condition and for suicidal ideation. All clinical findings and concerns will be discussed with the PI and adverse events will be reported to the IRB according to institutional guidelines.

This study is likely to have adverse events related to suicide attempts. Safety monitoring for adverse events (AEs) will be conducted in real time by the Principal Investigators and the research coordinators. The PIs will supervise the research and respond directly to patient problems. In the case of AEs, all of them will be indicated on the source documentation for the specific adverse event report form. The PIs will determine the severity of the event, will assign attribution to the event, and will monitor the event until its resolution.

How will you monitor adverse events? Adverse events will be monitored through regular contact with study participants, as well as contact with providers.

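### The CSSRS is rated weekly in PLF only, and the SAP does not say whether those ratings count towards the primary endpoint; if they do and recall is incomplete, the hazard ratio is biased modestly against PLF

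*Protocol*

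**What the plan says.** Protocol 13.b (list of tests and procedures) gives the CSSRS timing as "0, 3, 6,12, weekly for PLF group participants", in the "current & since last visit version". The count column of that row reads 4. No row gives TAU a weekly rating. A separate row, "PLF Intervention Sessions", is weekly with a count of 10. The unit of 0, 3, 6 and 12 is not printed; months is the natural reading, since the SAP refers to a one-year follow-up.

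The SAP's primary analysis is a Cox model with "incidence and time to the first suicidal behavior during the study course as the outcome variables". It names no instrument, visit set or event source, and gives no rule for dating events.

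Some other sources are not specific to an arm. "The Self-Injurious Thoughts and Behaviors Interview", the Beck Lethality Scale and the Suicide Intent Scale are listed at 0, 3, 6 and 12 (13.b). Item 16.b describes review by a study psychiatrist, real-time safety monitoring, and this: "Adverse events will be monitored through regular contact with study participants, as well as contact with providers". Item 16.c adds: "All suicide attempts and deaths will be reported to the JJPVA and the DSMB assembled for this study".

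The visit schedule is itself inconsistent. Item 9.b pays at baseline, post intervention, and 3 and 6 months after the intervention ends, which does not match 0, 3, 6 and 12.

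**The concern.** In a time-to-first-event analysis, an arm that is asked more often has more of its events recorded, unless every event is recalled at the less frequent visits. Followed literally, the SAP would count an event found only in a weekly PLF rating. The same event in TAU would count only if it was recalled at the next common visit or reached another source. The hazard ratio would then partly measure how often each arm was asked.

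The extra events fall in PLF, so a real benefit would be diluted. Randomisation and intention-to-treat do not remove this. Nor does the SAP's log-rank fallback, which uses the same events. Because the SAP is silent, the choice of which ratings count could be made after the data are seen.

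**Working it through.** **Inputs from Protocol 17.b:** TAU event rate 49%, 35% reduction, exponential hazards, 20% dropout, m = 5, ICC 0.01, N = 145. Item 13 gives half the participants randomised to PLF and 10 weekly groups.

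**The plan's own figure.** I take the 49% to be over 12 months.
- TAU hazard λ = −ln(0.51)/12 = 0.0561 per month.
- PLF rate = 0.49 × 0.65 = 0.3185, so the planned HR = ln(0.6815)/ln(0.51) = 0.569.
- At 80% power and two-sided 5% (assumed; not stated), the Schoenfeld formula gives 100 events. With exponential dropout and inflation 1 + 4 × 0.01 = 1.04, that is 284 participants, or 142 per arm.
- So 145 reproduces as a per-arm number but not as a total, although item 17.b uses it as a total (145 + 35 = 180). That is a separate matter; both readings are carried below.

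**Model for unequal recording.** Let s be the chance that an event is captured through the common visits and c the chance that a weekly rating captures it. Both are assumed, with c from 0.7 to 1.0. Events are dated by occurrence, and a missed event can be followed by a recorded one.
- TAU recorded hazard: s × λ throughout.
- PLF recorded hazard: [1 − (1 − c)(1 − s)] × HR × λ in weeks 1–10 (2.30 months), then s × HR × λ.

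**Hand check, true HR 1.** The share of 12-month first events falling in weeks 1–10 is (1 − exp(−0.0561 × 2.30))/0.49 = 0.121/0.49 = 0.247. At s = 0.8, the early ratio of recorded hazards is 1/0.8 = 1.25 (c = 1) or 0.94/0.8 = 1.175 (c = 0.7); afterwards it is 1. Weighting by the early share gives 1 + 0.247 × 0.25 = 1.06 and 1 + 0.247 × 0.175 = 1.04.

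**Large-sample Cox limits** (numerical integration; ranges for c = 0.7–1.0). Half recovery replaces s by s + 0.5(1 − s) in both arms.

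| Recall s | True HR 1, no recovery | True HR 1, half recovered | True HR 0.57, no recovery |
|---|---|---|---|
| 1.00 | 1.00 | 1.00 | 0.57 |
| 0.95 | 1.01 | 1.00–1.01 | 0.57–0.58 |
| 0.90 | 1.02–1.03 | 1.01 | 0.58 |
| 0.80 | 1.04–1.06 | 1.02–1.03 | 0.59–0.60 |
| 0.60 | 1.11–1.16 | 1.04–1.06 | 0.63–0.66 |

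If the weekly ratings do not count and the first common follow-up visit looks back to baseline, both arms have recorded hazard s × λ and the HR is 1.00 at every s.

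**Power at the planned effect, 145 per arm** (simulated; clustering and covariates ignored), common sources only versus weekly PLF findings counted:
- s = 0.8: 75% versus 66–68% with no recovery; about 80% versus 75–76% with half recovered.
- s = 0.6: 64% versus 42–49% with no recovery; about 74% versus 66–70% with half recovered.
- s = 0.90–0.95: a loss of at most about 4 points.
- If 145 is the total, s = 0.8, no recovery: 46% versus 38–40%.

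**Sensitivity to the model, true HR 1.** If a missed first event is never followed by a recorded one, s = 0.8 gives 1.07–1.10. Under that same assumption with complete weekly capture, it gives 1.21 if half of the TAU hazard fell in weeks 1–10. If events were dated to the detecting visit, perfect recall would still give 1.03.

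**The case against.** The strongest reply is that no passage sends the weekly ratings to the primary endpoint. The count of 4 matches the common visits, and the sessions have their own row with 10. The table therefore leans towards the weekly ratings being session monitoring, and on that reading there may be no bias. This stands: what is established is an open endpoint definition, not a biased result. But the row says both weekly and 4, and the SAP does not settle it.

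Second, capture outside the CSSRS is substantial and not arm-specific, and the post-intervention visit in item 9.b may put the first common recall soon after the 10 weeks. This also stands, and it makes the no-recovery power figures an upper bound on the loss. Recovery may still be partial. Item 16.c covers attempts and deaths, whereas item 17.b separates the composite from attempts alone, noting of a study of attempts that "the composite definition of suicidal behavior was not used". Item 16.c also lets clinicians delivering PLF trigger a suicide assessment, a route TAU does not have.

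Third, the bias is conservative for superiority, so keeping all events as primary with a common-source sensitivity analysis could be defended. That is a fair alternative, but its primary estimate would still mix treatment effect with frequency of asking.

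A reader might go further and infer from the since-last-visit form that weekly sessions shorten the month-3 look-back in PLF, losing early PLF events and favouring PLF. No passage says so; the look-back actually used only needs to be confirmed.

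**Conclusion.** The point holds conditionally. Scheduled ascertainment differs between arms, and the SAP does not confine the primary endpoint to what both arms receive. If weekly PLF findings count and recall at the common visits is incomplete, the hazard ratio moves against PLF: by a few per cent at recall of 0.8 or better under the protocol's constant hazard, and by 11–16% at 0.6, with about half of that left if other sources recover half of the missed events.

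The size rests on assumed recall, assumed weekly capture and the treatment of missed first events. Modest would be too mild a word if recall were much poorer or events clustered in the first 10 weeks; the documents give no figure for either. They do not support saying that the primary result will be biased, that it will favour PLF, or that the largest power losses above are to be expected. The change is worth making because it concerns the primary endpoint and costs little.

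**What to change.** In the SAP:
- Define the primary event from sources applied identically in both arms: the CSSRS and the Self-Injurious Thoughts and Behaviors Interview at the common visits, plus adverse-event reports collected the same way in both arms.
- State that each common visit covers the whole period since the previous common research visit, and that events are dated by occurrence.
- Report an all-sources analysis, including events found only through the weekly PLF ratings, as a sensitivity analysis.

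In the protocol, reconcile the weekly and 4 entries in the CSSRS row, and the visit schedules in items 9.b and 13.b. Confirm what look-back was used in PLF at the first common follow-up visit; where it was shorter than the full interval, disclose it. Weekly safety monitoring is unchanged.

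The cost is a few sentences and a check of existing records. There are two downsides. Some known PLF events move from the primary count to the sensitivity analysis. And PLF participants may recall events better at the common visits because they were asked weekly, which this change does not remove.
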